## 12 Study Management

This study will be managed according to ISO 14155:2011, the Declaration of Helsinki in its current revision, conditions imposed by local ethics committees (ECs), and any applicable regulatory requirements. For this study, the sponsor will have certain direct responsibilities and may delegate other responsibilities to appropriate consultants and/or contract research organizations (CROs). Together, the sponsor and all related participants will ensure that the study is conducted according to the above standards and all applicable regulations. All personnel to participate in the conduct of this clinical trial will be qualified by training, education and/or experience to perform his or her respective tasks.

### 12.1 Investigator Responsibilities

This section highlights responsibilities of the principal investigator (PI) at each site regarding this investigation. The PI, i.e., the main investigator at each study site, is responsible for managing day-to-day aspects of the study. The PI will take steps to ensure compliance with the CIP and

 
Cerus Endovascular
	
Document Number DNQS428-01
	
Rev. F
	
Page 48 of 119

Clinical Investigation Plan
	
Title
		

Confidential & Proprietary
	
Coil Assisted Flow Diversion: A prospective, single arm, multi-center study to assess the safety and performance of Neqstent in adjunctive therapy (CAFI Study)
		

associated documents and processes. The PI also protects data integrity and the rights, safety and well-being of clinical study subjects.

#### **12.1.1 Disclosure**

All investigators must disclose potential conflicts of interest, including financial interests, to the study sponsor, both before and during conduct of the clinical study as well as up to 1 year after the study has completed.

#### **12.1.2 Additional Site Team Members**

The site may add new members to the investigational team. Training of new personnel will be documented before new personnel participate in the study. New investigators should disclose potential conflicts, as described in Section 12.1.1.

#### **12.1.3 Communications with EC**

The site Principal Investigator (PI) and the site clinical study team are responsible for communication with site ethics committee if required. The Sponsor and/or designee is responsible for communication with central ethics committees if required. The PI will:

- provide the sponsor with copies of any relevant EC communications regarding this CIP
- comply with requirements from the EC regarding the CIP
- obtain written/dated approval/favorable opinion from the site EC, before starting the study or recruiting subjects
- obtain written/dated approval from the site EC before implementing any changes in a CIP amendment
- ensure the timeliness of safety reporting to the site EC
- promptly report deviations from the CIP to the EC that affect the rights, safety or well-being of the subject or the scientific integrity of the CIP
- keep all EC communications in its study file

#### **12.1.4 Informed Consent**

The PI is responsible for the informed consent (IC) process in this CIP. The PI will ensure that:

- the IC used for the consent process is the most current IC, has been approved by the EC and is consistent with any requirements imposed by the EC
- the IC process occurs consistent with ISO 14155:2011, and importantly, prior to any procedure specific to the clinical investigation is applied to the subject.
- a copy of the signed/dated IC form is kept in the subject's records
- either he/she or an authorized designee conducts the consent process consistent with ISO 14155

 
Cerus Endovascular
	
Document Number DNQS428-01
	
Rev. F
	
Page 49 of 119

Clinical Investigation Plan
	
Title
		

Confidential & Proprietary
	
Coil Assisted Flow Diversion: A prospective, single arm, multi-center study to assess the safety and performance of Neqstent in adjunctive therapy (CAFI Study)
		

### 12.1.5 Subject Identification Log

The PI or designee will maintain a log of all subjects enrolled in the study. The log links study identification (ID) numbers to identifying patient information (name, contact information). The log will be housed securely on site.

### 12.1.6 Compliance with CIP

The PI is responsible for ensuring that his/her site complies with the CIP. The PI will:

- maintain oversight of the study at the clinical site
- sign an investigator agreement form
- conduct the investigation in compliance with this CIP, applicable sections of ISO 14155:2011, and requirements of the EC to ensure the safety and well-being of study subjects
- create, maintain and make available source documents for study subjects
- not implement any change to the CIP without prior approval from the sponsor, local EC, and (if required) regulatory bodies if required
- not deviate from the CIP, except to maintain the subject's rights, protect the life and physical well-being of a subject in an emergency, or the scientific integrity of the investigation
- document all deviations from the CIP
- ensure that the site has adequate staff and capabilities
- ensure that site equipment used in the study is maintained and calibrated
- ensure the accuracy, completeness and timeliness of study data in CRFs and reports
- allow and support sponsor monitoring and auditing activities
- be available to monitors and the sponsor to address questions during study visits
- be available and support regulatory authorities during audits
- respond in a timely manner to sponsor inquiries
- make reasonable efforts to prevent early withdrawal
- make reasonable efforts to ascertain the reason for early withdrawal

 The sponsor may also document deviations from the CIP

 Cerus Endovascular	Document Number DNQS428-01	Rev. F	Page 50 of 119
Clinical Investigation Plan	Title		
Confidential & Proprietary	Coil Assisted Flow Diversion: A prospective, single arm, multi-center study to assess the safety and performance of Neqstent in adjunctive therapy (CAFI Study)		

### 12.1.7 Subject Records

The Investigator will maintain original source documents from which study-related data are derived, which include, but are not limited to:

- Clinic progress notes recording subject's medical history and medications
- Medical charts with operative reports and condition of subject upon discharge
- Medical records regarding AEs, including treatment and clinical outcome
- Results of diagnostic examinations
- Results of subject questionnaires
- Imaging (such as x-rays, angiograms, CTs, MRIs) as well as any existing reading or interpretation of diagnostic imaging
- Notes of phone calls and/or correspondence indicating investigational site's attempts to follow study subjects at the required follow-up visits until subject's participation in the study is complete or terminated
- Records relating to patient death (e.g., death certificate, autopsy report/terminal medical records)
- Printouts of source data generated by technical equipment (e.g., x-rays, angiograms) must be filed with the patient's records

### 12.1.8 Subject Accountability

The PI will make reasonable efforts to account for all study subjects, especially those who withdrew. If withdrawal is due to problems with study device safety or performance, the PI will obtain the subject's permission to follow his/her status/condition outside the clinical investigation, if possible.

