## 7.10 Early Withdrawal

Reasons for subject withdrawal prior to study completion shall be documented. Valid reasons for early study withdrawal include:

- Death
- AE or other medical condition that prevents study participation
- Withdrawal of voluntary consent
- Lost to follow-up (LTf)
- Termination of Study

At least three documented attempts shall be made to contact any subject who is LTF.

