## 7.11 Study Termination

The Sponsor has the right to terminate the Study. Reasons for Study termination shall be documented in the Clinical Investigation Report and Close-Out Monitoring Report. Valid reasons for study termination include:

- Administrative issues mandate termination
- Interim data analyses warrant study termination
- Regulatory action mandates termination

If the study is terminated for any reason, the governing Competent Authority and Ethics Committee shall be notified as applicable. If the study is terminated, all patients will remain in follow-up per the standard of care.

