## 7.12 Premature termination

The Sponsor reserves the right to discontinue the clinical trial/investigation at any stage (e.g. for safety reasons) or reduce the follow-up period with suitable written notice to the Investigator.

Possible reason(s) include:

Sponsor makes a final decision for the early termination of the clinical trial, or per DSMB recommendation

Further product development is cancelled.

Should the clinical trial be discontinued by the Sponsor, subjects will be followed up as per routine hospital practice.

In this case, the Investigator shall return all clinical trial/investigation materials (including devices) to the Sponsor and provide a written statement as to why the premature termination has taken place to the EC (if applicable) and inform subjects still participating to the trial. All applicable Clinical Investigation documents shall be subject to the same retention policy (the Investigators and/or designee(s) will be instructed to retain all study records required by the

 Cerus Endovascular	Document Number DNQS428-01	Rev. F	Page 39 of 119
Clinical Investigation Plan	Title		
Confidential & Proprietary	Coil Assisted Flow Diversion: A prospective, single arm, multi-center study to assess the safety and performance of Neqstent in adjunctive therapy (CAFI Study)		

Sponsor and regulatory authorities in a secure and safe facility, with limited access. All study material shall be stored for at least 10 years or as based on national regulations. The Investigator must request authorization from the Sponsor prior to destroying study records). Sponsor or designee will inform the CA about premature termination of Clinical Trial as per regulatory requirements

Study discontinuation:

The Study Completion/Discontinuation Form must be completed when:

- the subject is considered lost to follow-up (per the above definition) before the 24 months follow-up time point has been reached or
- the subject withdraws from the study or
- the Investigator withdraws the subject from the study or
- the subject has completed the study (at last Follow-up visit per protocol, the 24 months follow up visit).

The Sponsor shall be notified of the reason for subject discontinuation. The site will provide this information on the Study Completion/Discontinuation Form (e-CRF) and on source documents. Investigators must also report this to their EC if defined by their institution's procedure.

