### 8.2.2 AE causality:

Each AE shall be assessed by the Investigator for its relationship to the use of the study device or study procedure as follows.

- **Device Related:** Restricted to the study device.
- **Procedure Related:** Restricted to the implant procedure and any procedure associated directly with placement of the device.
- **Definitely related:** An AE is definitely related to a specific category if it is obvious, certain or there is little doubt regarding the relationship.
- **Possible related:** An AE is possibly related to a specific category if it is capable of being related but relatively unlikely.
- **Not related:** An AE is not related to a specific category if it is determined that there is no plausible association.

Subjects experiencing AEs shall be offered comprehensive medical care for conditions associated with the implant procedures and followed until their medical outcomes are resolved.

 Cerus Endovascular	Document Number DNQS428-01	Rev. F	Page 42 of 119
Clinical Investigation Plan	Title		
Confidential & Proprietary	Coil Assisted Flow Diversion: A prospective, single arm, multi-center study to assess the safety and performance of Neqstent in adjunctive therapy (CAFI Study)		

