## 10.2 Patient Population

Two patient populations will be considered in the analyses, an Intent-to-Treat (ITT) population and a Per Protocol population (PP). The ITT population includes all patients. The PP population will include subjects who complete 6 months of follow-up, die prior to their 6-month clinic visit, or are study failure (withdrawal from study to obtain alternate treatment). The PP will exclude patients with any major protocol violation that affects proper study inclusion or significant outcomes. Endpoints will be evaluated in the PP and ITT populations.

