## 10.4 Endpoints

### 10.4.1 Primary Endpoints

#### **Primary Safety Endpoint:**

The proportion of subjects with death of any non-accidental cause or any major disabling stroke within the first 30 days after treatment or major disabling stroke or death due to neurological cause from day 31 to 6 months after treatment.

Note: Major Disabling Stroke is defined as an episode of neurological signs or symptoms that persist beyond 24 hours accompanied with evidence of ischemia/infarction on imaging that results in an increase of NIHSS from baseline by  $\geq 4$  points and/or an increase from mRS baseline by  $>2$ .

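### Deaths and strokes after an outcome-related withdrawal or a sponsor stop may not reach the 6-month primary safety endpoint, because the plan does not require in-study collection after either

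*Combined protocol and SAP*

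**What the plan says.** The late part of the primary safety endpoint (section 10.4.1) is "major disabling stroke or death due to neurological cause from day 31 to 6 months after treatment". It therefore needs death and stroke status to 6 months for each treated subject.

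The rules on leaving the study are spread over several sections:

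- Section 7.10 lists among valid reasons for early withdrawal "AE or other medical condition that prevents study participation". Section 7.12 adds that the investigator may withdraw a subject.
- Section 10.2 describes one class of per-protocol subject as "study failure (withdrawal from study to obtain alternate treatment").
- Section 12.1.8 opens with a general duty: "The PI will make reasonable efforts to account for all study subjects, especially those who withdrew". For withdrawals caused by device safety or performance it then says that "the PI will obtain the subject's permission to follow his/her status/condition outside the clinical investigation, if possible".
- Section 7.11: "If the study is terminated, all patients will remain in follow-up per the standard of care". Section 7.12, which names safety reasons and a DSMB recommendation as grounds for stopping: "Should the clinical trial be discontinued by the Sponsor, subjects will be followed up as per routine hospital practice".

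The synopsis limits AE collection to the period from implantation to the end of the study. Section 10.6 defines the safety population as everyone implanted, bases the intent-to-treat analysis on whatever data exist for everyone enrolled, and rules out imputation. Section 11.3 rules out replacement of withdrawn subjects. Section 8.2.2 says that subjects with AEs are "followed until their medical outcomes are resolved".

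**The concern.** Three of the routes out of the study are tied to how the subject is doing: an AE, a device problem, or a need for alternative treatment. None of them implies that the subject refuses further data collection. Yet for device-related withdrawals the plan places follow-up outside the investigation and makes it conditional, and for the other two it requires no follow-up for new events. A subject who leaves at month 3 and has a major disabling stroke at month 5 has an endpoint event with no stated route into the data.

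Hearing of the stroke would not be enough. Section 10.4.1 defines a major disabling stroke by imaging evidence plus a change in NIHSS or mRS from baseline, and no section requires these to be recorded for the study once a subject has left.

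A sponsor stop raises a related problem. If the study is stopped because of suspected harm, follow-up is truncated in the people already carrying a permanent implant, when their 6-month status matters most. Section 10 says that the study is unpowered and rests on clinical judgement of descriptive rates, so an incomplete event count weakens its main safety output.

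**Working it through.** **1. The rules side by side**

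| Situation | What the plan provides | Are new events to 6 months required in the study data? |
|---|---|---|
| Device-related withdrawal | Follow-up outside the investigation, by permission, if possible (12.1.8) | Not stated |
| Withdrawal for an AE | Existing AEs followed to resolution (8.2.2) | Not stated for a new stroke or death |
| Withdrawal for alternative treatment | Kept in the per-protocol population (10.2) | Not stated |
| Sponsor stop | Standard of care (7.11) or routine practice (7.12) | Not stated |

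No section says that outcomes learned after withdrawal or a stop are entered, adjudicated or counted. No section excludes them either.

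**2. The plan's own numbers**

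Section 10.6 gives 46 subjects with 6-month data, 10% attrition and 51 enrolled. The 46 reproduces as the per-arm size of a non-inferiority comparison (55% against 70%, margin 10 points, one-sided 5%, power 80%): 45.26, rounded up to 46. Then 46 × 1.1 = 50.6, rounded up to 51. These figures are not disputed here. They are used only for the planned loss, 51 − 46 = 5 subjects.

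**3. Size per missed event**

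The documents give neither an expected safety event rate nor a rate of outcome-related withdrawal, so the event counts below are assumptions.

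- One event among 51 subjects: 1/51 = 2.0 points.
- Two events observed, one further event missed in one withdrawn subject: 2/50 = 4.0% reported, against 3/51 = 5.9%.

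**4. Extreme bound**

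Suppose that all 5 planned losses are affected and all 5 have an event:

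| Events seen in 46 | Available-case rate | Worst case over 51 | Gap (points) |
|---|---|---|---|
| 0 | 0/46 = 0.0% | 5/51 = 9.8% | 9.8 |
| 2 | 2/46 = 4.3% (exact 95% CI 0.5 to 14.8) | 7/51 = 13.7% (5.7 to 26.3) | 9.4 |
| 4 | 4/46 = 8.7% | 9/51 = 17.6% | 9.0 |

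**5. Study-wide stop (illustration)**

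Assume uniform accrual of 51 over 6 months, or 8.5 per month, with implantation at enrolment.

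- The DSMB review after 5 patients falls at 5/8.5 = 0.6 months, and the interim summary after 10 patients at 10/8.5 = 1.2 months. At either point nobody has 6 months of follow-up.
- At month 4, 8.5 × 4 = 34 are enrolled and none has 6 months of follow-up.
- At month 9, 51 − 8.5 × 3 = 25.5, so about half are still short of 6 months.
- From about month 12 (6 + 6), a stop costs this endpoint nothing.

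The direction of bias depends on the denominator. Take the month-4 stop with one event recorded. Dividing by all implanted subjects gives 1/34 = 2.9% and treats unknown status as event-free, which can only understate. Dividing by subjects who have either an event or complete 6-month status gives 1/1 = 100%, which overstates. The plan names the safety population but does not say how a subject without 6-month status enters the calculation.

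**The case against.** The best defence is that the plan is silent on these data rather than excluding them. Section 12.1.8 begins with a duty to account for withdrawn subjects, and its next sentence adds follow-up after they have left. Section 10.6 analyses all implanted subjects with all the data that exist. Section 12.1.7 lists death records among source documents, and section 12.2.11 requires the status of ongoing AEs at close-out. Sections 12.2.13 and 12.2.15 allow partial termination or temporary suspension, so a safety signal need not lead to a full stop. Section 10.6 also reports the number of values available, so a loss would be visible. The consent pages are not in the public document, and the data management plan and case report forms appear only as headings; they may say more.

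Part of this stands. A reader might infer that post-withdrawal events are excluded or certain to be lost; the documents support only that capture is not ensured. A reader might also see a flat contradiction with the synopsis, which has all implanted subjects completing the schedule, or with section 8.2.2. But the synopsis states the normal course and section 7.10 its exceptions, so this is a tension to reconcile. Nor does any section oblige a retreated subject to leave.

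The gap remains. Analysis-set definitions cannot supply data that nobody must collect. Section 8.2.2 and the close-out rule concern AEs that have already occurred, not a new stroke at month 5. Reporting the number available shows that values are missing, not what they were.

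**Conclusion.** The point holds as a gap in ensured capture. After a withdrawal due to an AE, a device problem or alternative treatment, endpoint events before 6 months may go unrecorded. Because these exits are linked to outcome, the safety rate is probably understated. Events before withdrawal are unaffected.

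A study-wide stop is different. It is not selective for subjects at highest risk: it truncates follow-up for everyone still under 6 months. A reader might infer that it too must bias the rate downward; that does not follow while the handling of subjects without 6-month status is undefined.

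Each missed event is worth about 2 percentage points among 51 subjects. The 9.8-point figure is not an estimate of this defect. It assumes that the whole 10% attrition allowance, which section 10.6 describes as loss to follow-up, is affected and that every such subject has an event. The month-4 stop is likewise only an illustration. The effect is on a descriptive rate, not on a hypothesis test.

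**What to change.** - **Sections 7.10, 10.2 and 12.1.8:** separate stopping study procedures or receiving alternative treatment from withdrawal of consent. For every implanted subject, with consent, continue in-study collection and adjudication of vital status, stroke, AEs and mRS through at least 6 months, by phone or record review if needed. State that these events count in the primary safety endpoint. Withdrawal of consent would still end collection.
- **Sections 7.11 and 7.12:** state that after a safety stop the same data continue to be collected in the study for all implanted subjects through at least 6 months. Reconcile this with the synopsis and section 8.2.2.
- **Section 10.6:** define how subjects without 6-month status enter the denominator, and add a worst-case sensitivity analysis that counts them as events. This also covers true losses to follow-up, whom continued collection may not recover.

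The cost is protocol and consent wording and remote follow-up of a few subjects. After a safety stop it is follow-up that was already planned. The reported safety rate may become slightly less favourable.

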### 12.1.9 Device Deficiencies and Malfunctions

Throughout the study, the PI or designee and sponsor will report and document all device deficiencies and malfunctions related to the identity, quality, durability, reliability, safety or performance of the device. This includes reporting of device deficiencies/malfunctions that did not lead to an AE but could have if: 1) suitable action had not been taken, 2) intervention had not been made, or 3) circumstances had been less fortunate.

The PI should make every effort to return devices suspected of deficiency or malfunction to the sponsor for analysis.

### 12.1.10 Medical Care

The PI will provide standard medical care to study subjects, including:

- informing the subject of a plan for further treatment including the treatment if the device is not implanted
- informing the subject of the nature and possible cause of any AEs experienced

 Cerus Endovascular	Document Number DNQS428-01	Rev. F	Page 51 of 119
Clinical Investigation Plan	Title		
Confidential & Proprietary	Coil Assisted Flow Diversion: A prospective, single arm, multi-center study to assess the safety and performance of Neqstent in adjunctive therapy (CAFI Study)		

- informing the subject of any new significant findings occurring during the clinical investigation, including the need for additional medical care that may be required
- providing the subject with medical care required for possible emergency situations related to the clinical investigation
- ensuring that clinical records are clearly marked to indicate that the subject is enrolled in this study
- providing, if required, the subject with documentation that the subject is enrolled in this study
- informing the subject's personal physician about the subject's participation in the study

